b) Initial Visit (at CHOA-Egleston)

Recruitment of the 20 to 40 pediatric subjects will take place at the Children's Healthcare of Atlanta at Egleston, when they are hospitalized with the diagnosis of new onset T1DM.

Enrolled participants will be interviewed in order to collect demographic information. The subjects will be randomized to either the FIXED group or the ICR group according to a computer-generated random sampling table. The subject and his/her caregivers will receive diabetes education while in the hospital in standard fashion. The subject and his/her caregivers will receive glucose monitoring education and training prior to hospital discharge. The subject and his/her caregivers will also receive a paper log to record the blood sugars, number of carbohydrates consumed, and insulin administered at each meal throughout the day.

Prior to discharge, all subjects will receive a regimen that includes a: 1) Meal-time insulin and carbohydrate regimen (# of units of insulin, # of carbohydrates, and/or ICR);

2) Evening dose of Glargine; 3) Hyperglycemia correction regimen for blood glucose levels > 199 mg/dL; and 4) Hypoglycemia treatment regimen for blood glucose levels < 70 mg/dL and/or symptomatic.

c) After Hospital Discharge and Between Clinic Visits

As per standard diabetes care, caregivers will report all blood glucose levels every day (to the study investigators) until the subject's initial clinic visit 4-6 weeks after diagnosis. All insulin adjustments will be made by the study investigators.

After the subject's first clinic visit, caregivers will contact the study investigators once a week to report blood glucose levels and the investigators will make adjustments as needed.

d) Diabetes Clinic Visits

All the diabetes clinic visits will occur at the Center for Advanced Pediatrics (CAP), approximately three miles from CHOA-Egleston Hospital. Subjects will attend clinic with one or more of the investigators approximately 1 and 4 months after enrollment.

At each clinic visit, subjects and their caregivers will answer standard diabetes questions, undergo a physical examination, and objective data (vital signs, glucose meter (GM) data, insulin dosing, and carbohydrate intake) will be collected by the study personnel.

B. STUDY POPULATION

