The primary goal of this study is to determine the feasibility of a subsequent clinical trial of rapid acting insulin dosing for fixed carbohydrates (FIXED group) vs ICR with variable carbohydrate intake (ICR group). In doing so, we will examine our ability to recruit and consent patients (>70% consent rate), study retention (>90% retention), completion of study visits (average session attendance \geq 90%), study measures (\geq 90% measure completion), caregiver treatment adherence, and post-treatment satisfaction (\geq 90%),

2) Secondary Outcomes Measures

Secondary outcome measures will include caregiver anxiety and glycemic variability. Each of these measures are described below.

One secondary outcome measure is caregiver anxiety. This will be assessed by a parental stress scale [17]. The caregiver will fill out the questionnaire at initial enrollment (prior to hospital discharge) and at each clinic follow-up throughout the study. We will use the Spanish adaptation of parental stress scale (PSS) [18] for Spanish population if necessary.

We clarify in the survey that the questions are to be answered in terms of how the caregiver-child relationship exists since the diagnosis of diabetes mellitus.

The scales are shown in **Annex 1 and 2**

Glycemic variability (GV) is another secondary outcome measure. The GV will be calculated in all subjects through the use of a glucose monitor (GM) data classification scale. Subjects will be considered to have appropriate GV if their blood glucose level is in the range of 80 mg/dL – 180 mg/dL (Group C).

The GV classification is as follows:

Group A: < 50 mg/dl.

Group B: 50 – 79 mg/dl

Group C: 80 – 180 mg/dl

Group D: 181 – 350 mg/dl

Group E: > 350 mg/dl

Safety is the last secondary outcome measure. The safety measured that will be compared in both groups include death, risk of life threatening event (i.e., severe hypoglycemia associated with seizure or altered mental status), hospitalization for diabetes complication (diabetic ketoacidosis or hypoglycemia), and risk of disability or permanent damage.

E. STATISTICAL CONSIDERATIONS

Randomization

Randomization will be performed by study statistician using random-permuted blocks of size 2 and 4. Randomization assignments will be placed in sealed, opaque envelopes to be stored. Study investigators will not be blinded to treatment assignment.

Sample Size

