Glycemic variability will be examined both as a continuous variable and a categorical variable using the ranges defined in section D. Time series analysis will be used to examine daily measures of blood glucose (obtained from patient diary's) during the study period. Variability will be measured as the probability of acute change (PAC), using methods described by Jahnig et al. (2008). Acute changes will be adjusted for time between readings. In addition, first-order autocorrelations and/or mean-square successive difference will be used to examine variation in readings as described by Jahnig. Multilevel modeling will be used to test between-group differences in variability.

Secondary Aim 3: Safety

Adverse event of interest and serious adverse events (see section D) will be summarized overall and by treatment group. For participants experiencing more than 1 episode of a specific event (e.g., severe hypoglycemia), the maximum grade and severity will be recorded. Chi-square tests will be used to compare the frequency of events between the two cohorts.

Given the exploratory nature of these secondary outcomes, we will calculate effect sizes based on the adjusted means and standard deviations or differences in proportions, when appropriate.

All analyses will be conducted using SAS v9.4 (Cary, NC).

F. ANTICIPATED RESULTS

This research will be feasible to develop a successful larger clinical trial. Due to the fixed regimen seeming to be less complicated, because there are less calculations to make than in those using the ICR group, we anticipate that parental anxiety will be decreased in the FIXED group. This will encourage more blood glucose monitoring and treatment compliance. Therefore, we anticipate GV to be decreased for the FIXED group.

G. LIMITATIONS

The major limitations of this study are related to caregiver's self-completion questionnaire and ability to contact study personnel frequently during the study period in order to report blood glucose levels and implement the insulin adjustments. More than likely, multiple insulin regimens should work, but the idea behind this study is that the fixed regimen may be easier to implement.

[figure not shown]

Figure 2: Proposed protocol.

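### The time-series measures of glycemic variability are taken from the handwritten diary although meter data are collected at each clinic visit, and no rule reconciles the two sources

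*Combined protocol and SAP*

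**What the plan says.** The combined protocol and SAP mentions glucose readings as study data in three places that matter here.

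- **Section 5.D, Secondary Outcomes Measures**, defines the outcome from the meter: "The GV will be calculated in all subjects through the use of a glucose monitor (GM) data classification scale". Groups A to E follow, with 80 to 180 mg/dL (Group C) as the acceptable range.
- **Section 5.A, Methods**, describes how readings are captured. At discharge, families "will also receive a paper log to record the blood sugars, number of carbohydrates consumed, and insulin administered at each meal". At the clinic visits at about 1 and 4 months, "objective data (vital signs, glucose meter (GM) data, insulin dosing, and carbohydrate intake) will be collected by the study personnel".
- **Section 5.E, Secondary Aim 2**, first sets out the two forms of the endpoint: "Glycemic variability will be examined both as a continuous variable and a categorical variable using the ranges defined in section D". The next sentence names the source for the time series: "Time series analysis will be used to examine daily measures of blood glucose (obtained from patient diary's) during the study period". The probability of acute change (PAC), first-order autocorrelation and/or mean-square successive difference (MSSD) come next in the same paragraph, together with this requirement: "Acute changes will be adjusted for time between readings". Multilevel models then compare the arms.

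Section 14 describes the meter as a finger-stick self-monitoring device. Diary and meter values therefore presumably record the same tests.

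**The concern.** The plan names the weaker of two records for the analysis that is more sensitive to the quality of the record. If diary and meter hold the same finger-stick results, they differ only through what happens between the meter display and the page: a value not written down, copied wrongly, or entered against the wrong time. A proportion of readings in range tolerates some of this. PAC, lag-1 autocorrelation and MSSD are built from pairs of neighboring readings, so one lost entry removes two pairs and creates a new one across a longer gap.

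Two things are at stake. First, the categorical result (meter) and the time-series result (diary) could rest on different sets of readings for the same child, and the plan gives no way to explain a disagreement. Second, section 5.E (Sample Size) intends the effect sizes from this pilot to inform later power calculations, so recording error would be carried into the planning of the next trial.

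**Working it through.** The plan gives no figure to reproduce on this point. The check is a comparison of the text, followed by two illustrations.

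**1. Source by measure**

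| GV measure | Source named | Where |
|---|---|---|
| Groups A to E | Glucose monitor data | 5.D |
| PAC, autocorrelation, MSSD | Patient diary | 5.E, Secondary Aim 2 |
| Rule if the two differ, or if the diary is incomplete | None | – |

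Meter data are already collected at both follow-up visits (5.A), so a meter-based time series needs no new measurement.

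**2. How one omitted entry acts on MSSD**

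MSSD is the sum of squared successive differences divided by the number of differences. As an illustration only, take the plan's own band limits as readings in mg/dL.

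- A peak is omitted. Full sequence 80, 180, 80: (100² + 100²)/2 = 10,000. Without the 180: 80, 80, so MSSD = 0.
- A reading on a rise is omitted. Full sequence 80, 180, 350: (100² + 170²)/2 = (10,000 + 28,900)/2 = 19,450. Without the 180: 80, 350, so MSSD = 270² = 72,900.

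The same kind of error lowers the measure in one case and raises it in the other. An adjustment for elapsed time can offset part of this only if the times are recorded correctly.

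**3. Whether the direction can be settled over many readings**

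It cannot be settled from the documents. A simulation with assumed inputs shows why. The assumptions are:

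- 6 readings a day for 120 days (720 per child);
- log-normal glucose, with child medians centered on 160 mg/dL (SD 0.15 on the log scale) and within-child log-SD drawn from a normal distribution with mean 0.4 and SD 0.08;
- first-order autoregression on the log scale;
- acute change set at the pooled 90th percentile of absolute successive differences, so that true PAC is 10%;
- recording error in one arm only.

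Shift in that arm, in between-child SDs:

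| Assumed diary error | Measure | Lag-1 correlation 0 | 0.3 | 0.6 |
|---|---|---|---|---|
| 20% of out-of-range values omitted | PAC | -0.11 | -0.05 | +0.01 |
| | MSSD | -0.10 | -0.04 | +0.04 |
| 20% of values replaced by uniform 100 to 180 | PAC | -0.22 | -0.08 | +0.22 |
| | MSSD | -0.20 | -0.06 | +0.29 |

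For scale, the standard error of a standardized difference near zero with 10 per arm is √(2/10) = 0.447. Every shift in the table is smaller than that, and the sign changes with the assumed correlation.

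**The case against.** The strongest reply is that nothing here is contradictory. Section 5.D ties a classification scale to the meter, and section 5.E ties a time series to the diary. That is one source per analysis, and both presumably record the same finger-sticks. This reading is available. It does not explain why the diary is preferred where order and timing matter most, and it leaves the two GV results resting on records that may differ.

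Three stronger readings are tempting, and the documents do not support them.

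- **No source is named for the continuous measure.** This is wrong. Secondary Aim 2 names the diary immediately before PAC, autocorrelation and MSSD, which are the only continuous variability measures in the plan.
- **The log lacks reading times, so the time adjustment cannot be done.** The log is described in one sentence and the form is not shown. It may have a time field, and the planned adjustment suggests that times were expected.
- **Caregiver reports are a third, unassigned data source.** Section 5.A mentions them, daily and later weekly, in the context of routine follow-up. Section 5.E never names them for analysis.

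It is also fair to say that frequent reporting to the investigators makes large-scale backfilling of the diary less likely, and that the simulated error rates are assumptions. Both points stand, and both limit the size of the concern.

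**Conclusion.** The point holds as a minor, cheap improvement. For measures built on consecutive readings, the plan names a handwritten record when the trial already collects a more objective one, and it has no rule to reconcile the two.

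The size of the effect is unknown. The documents give no rate of diary omission or of disagreement between diary and meter, no testing schedule and no cut-off for acute change. The simulated shifts show only that modest error need not have a predictable sign and, under those assumptions, stays below the sampling error of a 10-per-arm comparison. A reader might infer that the diary biases the comparison between FIXED and ICR. The documents do not show this, since nothing in them establishes that recording error differs between the arms.

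Section 5.E calls the secondary outcomes exploratory, and the primary aim is feasibility, so no main conclusion of the trial depends on this choice. The verdict assumes that diary and meter values come from the same finger-sticks and that the meter stores values with usable times.

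**What to change.** Replace the diary sentence in Secondary Aim 2 with text such as:

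> All GV measures, categorical and time-series, are computed from the glucose meter data collected at the 1- and 4-month visits, using the times recorded by the meter. Where meter data are missing, diary values may be substituted and are flagged. Substituted readings without a recorded time are left out of time-adjusted measures. A sensitivity analysis omits all substituted readings.

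Before enrollment, confirm that the meters' memory and clock settings cover the interval between visits. The documents describe neither. As a guide, about 90 days between the two visits at 6 to 10 readings a day gives 90 × 6 = 540 to 90 × 10 = 900 readings. The daily rate is borrowed from the Background section and is not a study schedule, so it is an assumption.

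The cost is a few sentences and a data export at two visits that already take place. The downside is dependence on meter memory and clocks. If memory falls short, either an earlier download is needed or more readings become fallback. The change removes recording error only: meter inaccuracy (section 14) and differences in how often families test remain.

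If the diary must be kept, the minimum is to name the source for each GV measure, state where reading times come from, and say which record prevails when they differ.

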Shortly after diagnosis of T1DM, many children and adolescents not uncommonly experience a honeymoon period [10]. It occurs because there is a sufficient amount of residual B-cell mass that enables some of these individuals to secrete some endogenous insulin. As a result, in order to prevent hypoglycemia, these individuals may be managed with less exogenous insulin over a short period of time [11]. This variability makes less accurate HbA1C concentration as a gold standard for assessing glucose control in the first 6-12 months after diagnosis [12,13].

Glycemic variability (GV) obtained from multiple blood glucose levels (up to 6 – 10 times/day) provides a good correlation for an individual's glycemic control and predictor of chronic diabetic complications [3]. The GV refers to swings in blood glucose levels and captures blood glucose oscillations that occur throughout the day, including hypoglycemic periods, postprandial increases, as well as blood glucose fluctuations that occur at the same time on different days [14]. The proposed target range of 70–180 mg/ dl is considered acceptable for clinical practice, as it has been observed that if 50% of the self-monitoring of blood glucose readings are in this range, the A1C would be ~7% [12,13]. Shapiro et al, reported that teens and parents show some similarities in the facets comprising distress, including negative emotions about diabetes and the demanding diabetes regimen [15]. Simplified insulin treatments will remarkably help to maintain adherence and to prevent deterioration in glycemic control.

For the purposes of this study the following definitions will be used:

BMI: Weight (kg)/ Height (m²).

Glycemic variability: Blood glucose oscillations that occur throughout the day. The glycemic range on target is between 80 – 180 mg/dl.

Insulin dose adjustment: Titration of insulin over time to improve glycemic control.

Parental stress: Stress associated to caring for a child with diabetes.

Insulin to carbohydrate ratio (ICR): Number of carbohydrates that 1 unit of rapid-acting insulin covers.

Basal insulin: Insulin that controls blood sugar consistently for 24 hours.

Rapid-acting insulin: Mealtime insulin. Typically has onset in 10 - 15 minutes, peaks at 45 – 60

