5. APPROACH –RESEARCH METHODS

A. STUDY DESIGN

Two - Arm, Randomized, Clinical trial (See Figure 1)

This proposal is designed to compare children and adolescents with newly diagnosed T1DM using a fixed insulin dose for fixed carbohydrate mealtime regimen (FIXED group) to children and adolescents with newly diagnosed T1DM using an ICR with variable carbohydrate intake (ICR group) mealtime regimen and determine:

1) Specific Aim 1

Determine the feasibility for a subsequent clinical trial involving rapid acting insulin dosing for a fixed dose for fixed carbohydrates (FIXED group) vs ICR with variable carbohydrate intake (ICR group) in order to determine the capacity for recruitment, caregiver consent to random assignment and completion of study measures, average session attendance, caregiver treatment adherence, and post-treatment satisfaction.

2) Specific Aims 2

- a) Determine if the caregivers of diabetics using a fixed insulin for fixed carbohydrate regimen (FIXED group) experience less anxiety than the caregivers of those using an ICR with variable carbohydrate intake regimen (ICR group) at 1- and 4-months post-randomization.
- b) Determine if diabetics utilizing a fixed insulin for fixed carbohydrate regimen (FIXED group) have decreased glycemic variability (GV) than those using an ICR with variable carbohydrate intake regimen (ICR group) at 1- and 4-months post-randomization.

We hypothesize that we will recruit and consent enough patients in order to perform a future, larger trial where caregivers of children and adolescents with newly diagnosed T1DM using a fixed insulin for fixed carbohydrate mealtime regimen (FIXED group) will experience less anxiety and their diabetic children will experience less GV than children and adolescents with newly diagnosed T1DM who use an ICR with variable carbohydrate intake at mealtime (ICR group). If this proves to be true, less anxiety may encourage more compliance and better glycemic control.

[figure not shown]

Figure 1: Study design and hypothesis.

3) Methods

a) Recruitment & Consent

Subjects with newly diagnosed T1DM will be evaluated by authorized study personnel under a HIPAA waiver to determine potential eligibility. The subjects will be contacted by the research study team while in the hospital during his or her initial diagnosis to explore his/her interest in the study and to confirm eligibility. The informed consent/assent documents will be signed at the time of the initial contact.

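### First-order autocorrelation is listed as a supporting measure of glycemic variation, but it does not measure the size of swings and has no valid direction for Aim 2b

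*Combined protocol and SAP*

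**What the plan says.** Section 4 (Background) describes the target: "The GV refers to swings in blood glucose levels and captures blood glucose oscillations that occur throughout the day". Aim 2b in section 5.A asks whether children on the fixed regimen "have decreased glycemic variability (GV) than those using an ICR with variable carbohydrate intake regimen", and section 5.F gives the expected direction: "we anticipate GV to be decreased for the FIXED group".

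The analysis is in section 5.E under Secondary Aim 2. It starts from diary readings: "Time series analysis will be used to examine daily measures of blood glucose". The lead measure comes next: "Variability will be measured as the probability of acute change (PAC"), with the rule that "Acute changes will be adjusted for time between readings". As an addition to PAC, "first-order autocorrelations and/or mean-square successive difference will be used to examine variation in readings", with a pointer to a 2008 methods source. The comparison is then given in one sentence: "Multilevel modeling will be used to test between-group differences in variability". Glucose is also analysed in the five ranges of section 5.D.

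The plan does not say which of these measures the multilevel model tests, whether a high or a low autocorrelation is favourable, or whether autocorrelation will be shown beside a variance or SD. Under Sample Size, section 5.E adds that an effect size will be derived for each measure of interest and used to power later work.

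**The concern.** The outcome concerns the size of swings, while autocorrelation concerns their order in time. A child with large, slow, smooth swings can have a high value, and a child with small, erratic ones a low value. No rule of the form *lower is better* or *higher is better* turns it into a measure of decreased GV.

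The wording nevertheless lists it as a way to examine variation, and *and/or* allows MSSD to be left out. Two things are then at stake. A between-group difference in autocorrelation, or its absence, could be offered as supporting evidence on Aim 2b when it says nothing about the size of swings. Its effect size, which could be near zero or of either sign despite a real reduction, could also be carried into the sizing of the larger trial that this pilot is meant to prepare.

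**Working it through.** The plan states no figure on this point, so there is none to reproduce. The check is algebra.

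**1. Scaling.** Lag-1 autocorrelation, r1, is the sum of products of successive deviations from the child's mean, divided by the sum of squared deviations. Multiply every deviation by a constant c: numerator and denominator both gain c², which cancels. So r1 is unchanged for any c, SD is multiplied by c, and MSSD by c². This needs no assumed values and holds with perfectly regular testing.

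**2. Unequal change in components.** Write glucose as a slow swing (SD S, lag-1 correlation φ) plus independent short-term noise (SD N). For a stationary series:

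- Var = S² + N²
- r1 = φS²/(S² + N²) = φ/(1 + N²/S²)
- MSSD = 2·Var·(1 − r1) = 2[S²(1 − φ) + N²]

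With φ and N above zero, r1 falls whenever S alone falls and rises whenever N alone falls. With φ below 1, Var and MSSD fall in both cases.

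Illustrative inputs, **assumed and not in the documents**: S = 60 mg/dL, N = 30 mg/dL, φ = 0.7.

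| Case | Var | SD | r1 | MSSD |
|---|---|---|---|---|
| Base | 3600 + 900 = 4500 | 67.1 | 2520/4500 = 0.56 | 2(1080 + 900) = 3960 |
| All swings halved | 900 + 225 = 1125 | 33.5 | 630/1125 = 0.56 | 2(270 + 225) = 990 |
| Slow swing halved | 900 + 900 = 1800 | 42.4 | 630/1800 = 0.35 | 2(270 + 900) = 2340 |
| Noise halved | 3600 + 225 = 3825 | 61.8 | 2520/3825 = 0.66 | 2(1080 + 225) = 2610 |

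MSSD falls by 75% (2970/3960), 41% (1620/3960) and 34% (1350/3960). Over the same three reductions r1 stays put, falls and rises.

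**3. Range.** For φ from 0.5 to 0.9 and N from 15 to 45, with S halved from 60 to 30, SD and MSSD fell in every combination and r1 fell too, by 0.07 (φ = 0.5, N = 15) to 0.30 (φ = 0.9, N = 45).

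**4. Why SD should stand beside MSSD.** MSSD mixes size and order. SD 60 with r1 0.6 gives 2 × 3600 × 0.4 = 2880, and SD 40 with r1 0.1 gives 2 × 1600 × 0.9 = 2880. At φ = 0.9 and N = 45, halving the slow swing takes SD from 75.0 to 54.1 but MSSD only from 4770 to 4230, or 11% (540/4770). MSSD responds in the right direction in every case above, but it does not give the overall spread on its own.

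**The case against.** The strongest reply is that little depends on this measure. PAC leads, autocorrelation comes only in addition, and the glucose ranges are analysed whatever is chosen under *and/or*. The outcome is secondary, section 5.E calls the secondary outcomes exploratory, and the study's purpose is feasibility. All of that stands and limits the weight of the point. A reader might infer that autocorrelation could become the only GV measure, or that the GV analysis as a whole is invalid. The documents do not support either reading.

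A second reply is that the plan nowhere equates low autocorrelation with instability. That stands too. A reader might infer that the plan would declare the calmer arm less stable, but the text gives no direction at all. The supportable criticism is that no direction can be valid: reading low as bad fails when the slow component shrinks, and reading high as bad fails when the noise shrinks.

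A third reply is that the cited methods source may pair autocorrelation with a variance or with MSSD. That source is not in the section 16 reference list, so the documents do not settle the matter. If pairing is intended, the plan should say so.

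A lighter edit would change *and/or* to *and*. This would guarantee that MSSD is reported. It would still leave autocorrelation listed as a measure of variation, open to testing and to being carried forward as an effect size.

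**Conclusion.** The point holds for a supporting exploratory measure. First-order autocorrelation is unaffected by the scale of the swings and can move either way when they shrink, so it cannot support or refute decreased GV under Aim 2b. The scaling result is exact. The directions in the component cases hold for any positive noise and any φ between 0 and 1. Only the sizes (0.56 to 0.35, or to 0.66) rest on the assumed S, N and φ.

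How often a trial would be misled depends on within-child and between-child variation that the documents do not give, so no frequency is claimed. The feasibility conclusions, PAC and the range categories are untouched. The wording is worth correcting before analysis because it leaves the choice and interpretation of this measure open until the data are seen, and because effect sizes from this pilot are meant to inform the next trial.

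**What to change.** In section 5.E, Secondary Aim 2:

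- Remove first-order autocorrelation as an alternative measure of variation. Name MSSD, together with the within-child SD, as the supporting measure beside PAC.
- Report autocorrelation only descriptively, as a measure of temporal dependence, in the same table as SD and MSSD.
- State that no Aim 2b between-group test, conclusion or effect size for the future trial rests on autocorrelation.
- In the multilevel modelling sentence, name the measure tested and the direction that counts as decreased GV.

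The cost is SAP wording only. SD and MSSD come from the diary readings already planned, so no new data, visits or participants are needed.

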A goal of 20 patients is necessary for this study, but we will reach up to 40 participants in case there is any withdraw after consented and randomized. While the overall goal of the study is to demonstrate feasibility of a subsequent randomized controlled trial, limited efficacy testing will be performed. Given a sample size of 20 participants (10/grp), we will have greater than 90% power to detect a minimum standardized mean difference of 1.25 (i.e., approximately a 1.25 standard deviation difference) between groups. Effect sizes will be calculated for all study measures of interest and be used in future power calculations. On average, there are ~25 new type I/II diabetics diagnosed at Egleston hospital each month. Assuming an eligibility rate of 40%, 10 patients would be eligible to participate each month. Based on this, we are confident in our capacity to recruit 20 to 40 participants during the study period with the goal of having 20 participants to complete the study.

Statistical Analysis

Demographic characteristics will be summarized for both groups using means and standard deviations, medians and quartiles, or counts and percentages, as appropriate based on distribution. T-tests, Wilcoxon rank sums, and/or Chi squared tests will be used to assess differences between the two groups.

Primary Aims: Measures of feasibility (consent, retention, engagement, satisfaction, etc.), will be summarized overall and by group, when applicable.

Secondary Aim 1: Parental stress scale

The parental stress scale will be scored per the instrument's instructions. The total scores for the treatment groups will be compared in a cross-sectional fashion using t-tests or Wilcoxon rank sums tests as appropriate based on the distribution of scores. Changes in parental distress over-time will be evaluated using two-way repeated measures analysis of variance models. Models will include the main effect of treatment assignment, time (baseline, 1 month, 4 months), and the treatment X time interaction. The interaction term will serve as the primary statistical test for aim 2. Summary statistics, statistical significance, and effect sizes will be reported by group at each time point of interest, when applicable.

Secondary Aim 2: Glycemic variability

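### No time adjustment is stated for MSSD and first-order autocorrelation, so a difference in testing frequency between arms can pass for a difference in glycemic variability

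*Combined protocol and SAP*

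**What the plan says.** Section 5.E, Secondary Aim 2, takes glycemic variability (GV) from "daily measures of blood glucose (obtained from patient diary's) during the study period". The lead measure is the probability of acute change (PAC), and for it the plan says "Acute changes will be adjusted for time between readings". The next sentence adds that "first-order autocorrelations and/or mean-square successive difference will be used to examine variation in readings", following the same external methods paper, and repeats no adjustment. The comparison between arms is then described in one line: "Multilevel modeling will be used to test between-group differences in variability". No covariate for interval or testing frequency is named.

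The number and clock times of tests are not fixed. Section 4 mentions "Glycemic variability (GV) obtained from multiple blood glucose levels (up to 6 – 10 times/day", but as background on how GV is measured. Section 5.A.3 gives every family a log for blood sugar, carbohydrate and insulin at each meal. Glucose values are reported daily until the first clinic visit and weekly after it.

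Of lower caregiver anxiety under FIXED, Section 5.F says "This will encourage more blood glucose monitoring and treatment compliance", and then "Therefore, we anticipate GV to be decreased for the FIXED group". Section 5.G does not list unequal testing as a limitation.

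**The concern.** MSSD and lag-1 autocorrelation both compare each reading with the one before. If glucose values close in time resemble each other, closer readings lower MSSD and raise autocorrelation although the child's glucose behaves exactly as before. The plan recognises the spacing problem for acute changes but states no remedy for two statistics that share it.

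The plan also predicts a spacing difference between arms, in the direction that would favour its own hypothesis for Specific Aim 2b. Section 5.E (Sample Size) says that effect sizes for all measures of interest will be used in future power calculations. A testing-frequency artefact could therefore help to size the larger trial.

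**Working it through.** **The plan's own figure.** The plan gives no figure for MSSD or autocorrelation. Its only design calculation is "Given a sample size of 20 participants (10/grp), we will have greater than 90% power to detect a minimum standardized mean difference of 1.25". With a two-sided 5% test this gives 75.3% (t) or 79.8% (normal), so it is not reproduced on those terms. That is a separate matter, and nothing below depends on it.

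**Inputs.** From the documents: 10 children per arm, diary readings, more monitoring expected in FIXED (size not given). Assumed, because the documents give none: glucose SD 70 mg/dL (cancels in ratios), correlation time τ of 2–4 h, 4 to 6 tests per day, and the same stationary first-order autocorrelated glucose process in both arms.

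**Formulas.** For readings Δ hours apart:
- lag-1 autocorrelation = exp(−Δ/τ)
- MSSD = 2·SD²·(1 − exp(−Δ/τ))

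**Step 1: tests evenly spaced over 24 h.** Δ is 6 h for 4 tests, 4.8 h for 5 and 4 h for 6.

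| τ | Autocorrelation at 4, 5, 6 tests/day | MSSD ratio 6 v 5 | MSSD ratio 6 v 4 |
|---|---|---|---|
| 2 h | 0.050, 0.091, 0.135 | 8474/8911 = 0.95 | 8474/9312 = 0.91 |
| 4 h | 0.223, 0.301, 0.368 | 6195/6848 = 0.90 | 6195/7613 = 0.81 |

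**Step 2: tests in waking hours only.** Spread over 07:00–22:00, the daytime gaps are 3 h (6 tests), 3.75 h (5) or 5 h (4), with a 9 h overnight gap. At τ = 4 h, the mean of 1 − exp(−Δ/τ) is:
- 6 tests: (5×0.528 + 0.895)/6 = 0.589
- 5 tests: (4×0.608 + 0.895)/5 = 0.666
- 4 tests: (3×0.714 + 0.895)/4 = 0.759

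The MSSD ratios are 0.589/0.666 = 0.88 for 6 v 5 and 0.589/0.759 = 0.78 for 6 v 4.

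**Step 3: simulated trials with no true difference.** These used 10 per arm, 28–30 days, τ of 2–4 h, several settings for between-child spread, and a two-sided 5% t-test on per-child summaries. The nominal rate favouring FIXED is 2.5%. With 200 trials per scenario, the standard error at that rate is √(0.025×0.975/200) = 1.1 percentage points.

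| Tests/day, FIXED v ICR | Fall in MSSD | MSSD falsely favours FIXED | Autocorrelation falsely favours FIXED |
|---|---|---|---|
| 5 v 5 | about 0 | 1–3.5% | 1–5% |
| 6 v 5 | 6–14% | 4.5–18% | 27–64% |
| 6 v 4 | 13–27% | 11–62% | 77–100% |

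The overall SD of glucose stayed at 70–71 mg/dL in both arms, which confirms that only the spacing had changed. In the runs with 25% between-child spread in SD and in τ, 6 v 4 gave a spurious standardized difference of about −0.3 to −0.4 for MSSD and 1.3 to 1.55 for autocorrelation. The second exceeds the 1.25 that the study is sized to detect.

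**Step 4: candidate remedies.**
- Dividing squared differences by elapsed time overcorrects. At τ = 4 h with even spacing, 6 tests give 6195/4 = 1549 and 4 tests give 7613/6 = 1269, a ratio of 1.22 against FIXED. Simulated ratios with unequal testing ran from 1.08 to 1.56.
- Restricting to common daily slots gave ratios of 0.96–1.03, with 0–5% of trials falsely favouring FIXED.

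**The case against.** Several counter-arguments have force.

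- **The cited method.** A reader might infer that the plan makes no time adjustment for these statistics. The documents do not show that. They defer to a methods paper, which may contain one. What stands is that no adjustment is stated, directly after one is stated for acute changes.
- **The contrast.** A reader might take 6 v 10 tests per day as the difference between arms. Section 4 gives that range as background only, and Section 5.F gives no size.
- **Shared anchoring.** Both arms keep a mealtime log and report in the same way. If more monitoring only means fewer missed readings, the MSSD effect is small: with four daily slots completed 90% v 80% and τ of 2–6 h, the ratio was 0.97–0.98 and rejection 4–6%. Autocorrelation was not checked in that setting.
- **Direction.** A reader might infer that the bias must favour FIXED. That needs extra tests unrelated to glucose level. When tests triggered by extreme values were added to FIXED only, the MSSD ratio was 1.13, 1.08 and 0.95 at τ of 2, 3 and 6 h. Testing behaviour still confounds the comparison, but the sign is not fixed.
- **The test.** The simulations used t-tests, while the plan names multilevel modelling. The shift in MSSD and autocorrelation does not depend on the test, and a model with no term for spacing would carry it forward.
- **Standing.** These are add-on, exploratory measures. PAC leads and is time-adjusted, GV is also analysed by glucose range, and the primary goal is feasibility.

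**Conclusion.** The point holds as a gap in specification. As written, the plan states no protection for MSSD and first-order autocorrelation against unequal testing, and it expects unequal testing. If FIXED families test more, for reasons unrelated to glucose level, both statistics shift in favour of FIXED with no true difference.

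The size is conditional on a correlation time of 2–4 h and on testing rates that the documents do not give. With one extra test per day, the inflation of false positives for MSSD is modest, and at its low end barely separable from simulation error. With two extra it is clear. Autocorrelation is badly affected even by one.

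The documents do not support reading this as overturning Specific Aim 2b, which does not rest on these two statistics alone. The practical harm is a misleading effect size passed to the next trial. It should be corrected before analysis, but it does not threaten the pilot's primary purpose.

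**What to change.** Add to Section 5.E, Secondary Aim 2, wording to this effect: MSSD and lag-1 autocorrelation will be computed in both arms only on a common set of daily slots (for example pre-meal and bedtime readings already logged), using within-day pairs of adjacent slots with both readings present. Requiring both readings keeps missed tests from widening the intervals in one arm. Interval-matched pairs or a continuous-time model would also serve.

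Do not divide squared differences by elapsed time. Do not define the autocorrelation on successive differences either, since that is a different statistic from the autocorrelation of readings. If the cited paper's adjustment is intended for these measures, say so and describe it.

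Report readings per day by arm beside the results.

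The cost is a sentence or two of analysis text and a little programming, with no change to what families are asked to do. The small downside is that off-schedule readings drop out of these two statistics. They remain available for PAC and the glucose-range summaries.
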